### 7.1.2 Sensitivity Analyses

**For missingness** The main analysis is based on the “Main analysis set A”, which does not include patients for whom the primary endpoint is missing. This choice may be anti-conservative if the reason for drop-out was related to the outcome and differed between arms. For this reason, we will use the causal bounds from Gabriel et al. [5] for the effect given in equation 2 and the best-case/worst-case bounds equation 3 of the same paper if there are any missing composite outcome values based on “Main analysis set B” detailed in Section 6. If there is additional noncompliance, we will use the equivalent bounds for the per-protocol effect, as this can sometimes give large intervals. Given the conservative nature of the bounds, we will not further place confidence intervals on them unless it is deemed necessary for publication, in which case exact confidence intervals will be used.

**For mechanistic imputation** The composite outcome may have some form of “mechanistic” imputation, i.e. residual area stenosis  $>20\%$  is determined by direct measurement (OCT) of, if necessary, by quantitative coronary angiography. Values indicating residual area stenosis  $>20\%$  from OCT or angiography are considered reliable, however, particularly with quantitative coronary angiography, missing OCT analysis due to poor image quality or failure to obtain OCT is possible and may be related to residual area stenosis. Thus, we will impute all “mechanistic” imputed residual area stenosis that were found to be  $<20\%$  to be  $>20\%$  to determine the impact that missed OCT analyses could cause. Additionally, all patients without true measure of no event, that were adjudicated to have no event for the primary analysis, will instead be imputed to have an event and the impact of the adjudication will be determined by rerunning the primary analysis.

As part of the sensitivity analysis, we will adjust individually and collectively, if possible, for several variables known to be strongly predictive of the composite outcome but not used as stratifying variables for randomization. Thus, if by chance they are imbalanced in randomization, adjustment for them may reduce the effect of interest. In each regression, we will also adjust for site, with an indicator for each site that has at least three events and combining sites that are geographically close as needed when less than three events have occurred within a site. This will provide the correct standard error estimates since the randomization was stratified by site. For this reason, the results may be more significant or significant when the primary analysis is not, regardless of the results of the sensitivity analysis adjusting for site; this analysis will not replace the primary analysis in the publication as it does not strongly control the type I error rate. The additional variables include:

- Presentation (acute vs. chronic)
- Prior revascularization
- Diabetes mellitus
- LAD vs non-LAD

Logistic regression, including both main effects and interactions with treatment assignment, will be considered whenever possible; we will obtain marginal risk ratios via standardization (g-computation). Example code is provided in the code section 9.2. If this is not possible, i.e. the method will not converge due to the lack of events, we will run a main effect only model.

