### 3.1 Objectives, Endpoints, and Estimands

#### 3.1.1 Primary

The primary objective is to show that the use of balloon lithoplasty for routine lesion preparation is superior to the current conventional techniques used for routine lesion preparation before implantation of newest-generation drug-eluting stents in severely calcified coronary lesions. The primary outcome is a composite of measures indicating procedural failure and 1-year target vessel failure. Specifically, the two intervention being compared are:

- Routine lesion preparation with balloon intravascular lithoplasty (IVL) with or without the use of rotational atherectomy at the operators discretion, and
- Routine lesion preparation with conventional techniques using conventional balloons, modified balloons, or high-pressure balloons with or without the use of rotational atherectomy at the operators discretion

prior to implantation of newest-generation drug-eluting stents in severely calcified coronary lesions. After the procedure, patients are followed for one year to determine the primary composite endpoint. The primary composite endpoint is determined by the following:

- Failed or no stent delivery determined by the angiographic core laboratory.

Failed or no stent delivery is defined as failure to deliver and deploy 1 or more coronary stents to cover the intended length of the intended target lesion.

- OCT-assessed residual area stenosis  $\geq 20\%$ .

Residual area stenosis is defined as  $1 - [\text{in-stent minimal lumen area (MLA)} / \text{reference lumen area}]$ . Residual area stenosis will be determined primarily by OCT, or, if necessary, by quantitative coronary angiography, as defined in the OCT and quantitative coronary angiography definitions section of the protocol. The use of angiography is a form of imputation and we will investigate the impact of this in Section 7.1.2.

- Target vessel failure within one year.

Defined as cardiac death, target vessel-related myocardial infarction, or clinically driven target vessel revascularization.

- Cardiac death is defined as death due to coronary heart disease, sudden cardiac death, heart failure including cardiogenic shock, and death related to the cardiac procedure within 28 days from the procedure. If death is not clearly attributable to other non-cardiac causes, it is adjudicated as cardiac.

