## 8 Sample Size Determination and Power Calculation

In the protocol, it was stated that to reach 80% power to detect a true difference of 15%, with 25% in the standard of care group and 10% events in the IVL group for a two-sided test with alpha of 0.05, 194 patients total, 97 per arm, are needed when randomized 1:1. However, it was planned to enroll 200 patients to allow for a low level of loss to follow-up.

Instead, when using the intended exact method, we find that 194, 97 per arm, only provides 78% power for the hypothesized true difference in risks. Using the intended enrollment of 100 per arm, we reach the desired 80% power. These power calculations were carried out using the Power2x2 function, as outlined below.

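### The check on QCA-substituted and adjudicated negatives recodes both arms together, so how hard it tests the arm comparison depends on an unknown split, and the case unfavourable to IVL is never run

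*SAP*

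**What the plan says.** SAP section 3.1.1 has residual area stenosis read by OCT or, where necessary, by QCA, and is open about the status of the second route: "The use of angiography is a form of imputation and we will investigate the impact of this in Section 7.1.2".

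Section 7.1.2, under mechanistic imputation, accepts that OCT may be missing for reasons linked to residual stenosis. Its response is to turn all QCA-based values below 20% into values above 20%, "to determine the impact that missed OCT analyses could cause". The next sentence deals with adjudication: "Additionally, all patients without true measure of no event, that were adjudicated to have no event for the primary analysis, will instead be imputed". Those patients are thus counted as events, and the primary analysis is rerun. Neither sentence distinguishes the arms.

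The preceding paragraph of 7.1.2 handles missing composite outcomes differently. It recognises that drop-out can mislead when it is related to outcome and differs between arms, and it plans causal bounds and best-case/worst-case bounds, but only for patients whose composite is missing.

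The claim being tested is comparative. Under section 7.1.1, superiority needs p ≤ 0.05 and a risk ratio (RR) below 1.

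**The concern.** A recode in one direction in both arms answers one question: what happens if every unverified negative was really an event. It does not bound a comparison between arms. If the conventional arm holds clearly more of these readings, the recode adds more events there, and the rerun can look stronger for IVL than the primary analysis did. The opposite case, in which substituted negatives conceal failures in the IVL arm while those in the conventional arm are correct, is not run.

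The bounds do not close the gap. They apply to missing composites, whereas QCA or adjudication completes the composite for these patients. The imaging exclusion from analysis set A (section 6) could be read as removing anyone who lacks either modality. Sections 3.1.1 and 7.1.2 make sense only if QCA-only patients stay in.

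At stake is what the report can say about changing the instrument. A smaller p-value from this rerun could be read as robustness although the adverse case was not examined.

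**Working it through.** **Inputs from the SAP.** Section 8 assumes a true difference "with 25% in the standard of care group and 10% events in the IVL group", for a "two-sided test with alpha of 0.05". Appendices 9.1 and 9.2 specify an unconditional exact test on the risk ratio with FisherAdj ordering and no mid-p. The SAP gives no rate of OCT failure and no number of adjudicated negatives, so every such count below is an assumption.

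**Reproducing the plan's figures.** The protocol size is stated as "194 patients total, 97 per arm, are needed when randomized 1:1". The unpooled normal formula gives n = (1.960 + 0.842)² × (0.10×0.90 + 0.25×0.75) / 0.15² = 7.85 × 0.2775 / 0.0225 = 96.8, so 97 per arm. For the exact test the SAP says that 97 per arm "only provides 78% power for the hypothesized true difference in risks", and "Using the intended enrollment of 100 per arm, we reach the desired 80% power". A re-implementation (Fisher mid-p ordering, maximised over the common rate, central two-sided p) gives 78.2% and 80.3%. Both figures reproduce, so this version of the test is used below.

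**Algebra.** Let a and b be the observed events in the IVL and conventional arms, each of size n, and q1 and q2 the substituted negatives recoded in each.
- Risk difference after the recode: (a − b + q1 − q2)/n. With IVL ahead, it widens whenever q2 > q1.
- Risk ratio after the recode: (a + q1)/(b + q2). It is below a/b only if q1/q2 < a/b.

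**Scenarios.** 100 per arm; 10 vs 25 events before any recode: RR 0.40, difference 15 points, p = 0.0057.

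| Recoded (IVL, conv.) | Both arms, as planned | RR | Diff. (points) | p | IVL arm only | RR | p |
|---|---|---|---|---|---|---|---|
| 5, 5 | 15 vs 30 | 0.50 | 15 | 0.013 | 15 vs 25 | 0.60 | 0.080 |
| 10, 10 | 20 vs 35 | 0.57 | 15 | 0.019 | 20 vs 25 | 0.80 | 0.44 |
| 8, 10 | 18 vs 35 | 0.51 | 17 | 0.0067 | 18 vs 25 | 0.72 | 0.24 |
| 5, 10 | 15 vs 35 | 0.43 | 20 | 0.0011 | 15 vs 25 | 0.60 | 0.080 |
| 4, 10 | 14 vs 35 | 0.40 | 21 | 0.0005 | 14 vs 25 | 0.56 | 0.056 |
| 3, 10 | 13 vs 35 | 0.37 | 22 | 0.0003 | 13 vs 25 | 0.52 | 0.032 |
| 10, 5 | 20 vs 30 | 0.67 | 10 | 0.11 | 20 vs 25 | 0.80 | 0.44 |

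Boschloo's test gives 0.0006 for 14 vs 35 and 0.056 for 14 vs 25.

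**Thresholds from 10 vs 25.** With q1 = 4, the p-value falls below its starting value once q2 reaches 6, and the RR falls only once q2 reaches 11. With q1 = 5 the figures are 7 and 13. With q1 = 10, the p-value needs q2 of at least 13.

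**Equal counts.** The planned p-value rises slowly, to 0.024 with 14 recoded in each arm. Recoding the IVL arm alone loses significance at four.

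**A non-significant start.** 10 vs 20 gives p = 0.056. Recoding 5 and 10 gives 15 vs 30 and p = 0.013, with the RR unchanged at 0.50.

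**The case against.** Four points can be made for the plan.

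1. A reader might infer that any excess of OCT failure in the conventional arm makes the check favour IVL. It does not. Recoding 8 and 10 weakens both the RR and the p-value, and 5 and 10 moves the RR slightly towards 1 while the p-value falls. The RR is the SAP's primary measure, and it needs a large imbalance before it drops. If OCT fails more often in the IVL arm, the check is conservative. This stands and sets the limits of the point.

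2. A reader might also infer that OCT will fail mainly in tight, poorly prepared lesions and hence in the conventional arm. The SAP says only that missing OCT may be related to residual stenosis. It says nothing about arm. Failed stent delivery and QCA stenosis of at least 20% already count as events, so an excess of QCA negatives in the conventional arm does not follow. This stands too: the direction is unknown.

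3. The SAP does not claim that the check proves robustness. Its stated aim is to gauge impact, and it sets no criterion. True, but an impact on a comparison cannot be judged from a single joint recode.

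4. Recoding the IVL arm alone assumes every substituted negative is wrong there and right in the other arm, although outcome assessment is blinded (section 4.1). That is extreme, and it argues against using the rerun as a pass/fail rule. It does not argue against reporting it as one end of a range.

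**Conclusion.** The point holds in a limited form. The recode in 7.1.2 applies to both arms at once, its severity as a test of the comparison depends on an arm split that the SAP does not give, and no planned analysis sets these patients against IVL. At the design rates with 100 per arm, four substituted negatives in the IVL arm are enough to lose significance when recoded alone (p = 0.056), while the planned rule with four and ten reports a p-value about ten times smaller than the primary one (0.0005 against 0.0057) at an unchanged RR of 0.40.

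The sizes rest on assumed counts, on full enrolment without loss, and on observed events equal to the design rates. The documents do not show that the check will favour IVL, only that it can, and that with equal or nearly equal counts it is mildly conservative. The primary test is not affected.

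**What to change.** In section 7.1.2, keep the both-arms recode and prespecify two further reruns of the primary analysis: QCA-based and adjudicated negatives recoded to events in the IVL arm only, and the same in the conventional arm only. A two-way tipping-point grid over the two arms would serve equally well. Report the number of QCA-substituted and adjudicated readings by arm beside the results. Present the IVL-only rerun as the unfavourable extreme, without making it the sole criterion for robustness. Fix this before the arm split of these readings is known.

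The cost is two more runs of the code in Appendix 9.2 and a sentence or two in the SAP. The downside is that the stated robustness may look weaker.

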## 7.2 Additional Analysis

In addition to the primary analysis based on the risk ratio of the composite primary endpoint and the risk difference of non-cardiac deaths, we will display cause specific cumulative incidence using time to the composite endpoint. If there is not competing risk of non-cardiac death, these will instead be the kaplan-meier curves.

## 7.3 Secondary Endpoints Analyses

For binary secondary safety endpoints we will use chi-squared tests, as we are more concerned with type II errors, i.e. not observing a true safety signal over making a type I error. Just as with the primary composite endpoint, we will never report findings for the secondary endpoints without the competing risk of death not included in the endpoint. For continuous outcomes we will use linear regression adjusting for site.

We will use the datasets numbered in the same manner as the safety outcome as detailed in Section 6 for each of the secondary safety analyses, as follows: The justification for this is that unlike efficacy secondary analysis that we would like to be comparable to the primary results and using the same dataset, for safety we will use all available data.

### Safety endpoints

1. In-hospital and 1 year major adverse cardiac events and its components:
  - 1a Cardiac death at or before one year after the index procedure
  - 1b Any myocardial infarction at or before one year after the index procedure
  - 1c Stroke at or before one year after the index procedure
2. In-hospital procedure events
  - 2a Periprocedural myocardial infarction
  - 2b Coronary dissection (beyond intended by lesion preparation)
  - 2c Coronary perforation/rupture

For binary efficacy endpoints we will use the same exact testing as for the primary composite end point for binary outcomes and site adjusted linear regression for continuous outcomes. For all secondary efficacy analyses we will use the “Main analysis set A” detailed in Section 6, to make the results comparable and on the same set as the primary.

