## 6 Analysis Sets

- The “**Main analysis set A**” consists of all randomized participants who have a complete measure of the primary composite endpoint. This will exclude three groups of patients: patients who withdraw consent prior to 1 year and explicitly do not wish to participate in the 1-year clinical follow-up data collection, patients that are deemed to be lost to follow-up by the Clinical Endpoint Adjudication Board (see section 4.3 of protocol version 5.3), and patients who lack baseline OCT or Quantitative coronary angiography.
- The “**Sensitivity analysis set or Main analysis B**” consists of all randomized participants.
- **Secondary Safety endpoint analysis set 1, 1a, 1b, 1c:** consists of all randomized participants who have a measure of in-hospital and 1 year major adverse cardiac events for set 1, all randomized participants who have a measure of Cardiac death at or before one year after the index procedure, 1a, all randomized participants who have a measure of any myocardial infarction at or before one year after the index procedure, 1b, and all randomized participants who have a measure of stroke at or before one year after the index procedure, 1c.
- **Secondary Safety endpoint analysis set 2, 2a, 2b, 2c:** consists of all randomized participants who have a measure of in-hospital procedure events overall, 2, of periprocedural myocardial infarction, 2a, coronary dissection (beyond intended by lesion preparation), 2b, and coronary perforation/rupture, 2c. As it is very likely that all randomized participants will have measures of these events or be followed to know that the event did not occur, all of these groups may be the same as “Sensitivity analysis set or Main analysis B”

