### Efficacy endpoints

1. Components of the primary composite endpoint:
  - 3a Failed or no stent delivery
  - 3b Residual area stenosis  $\geq 20\%$
  - 3c Target vessel failure within one year
2. Components of target vessel failure at or before 1 year:
  - 4a Cardiac death.
  - 4b Target vessel-related myocardial infarction
  - 4c Clinically driven target vessel revascularization.
3. OCT endpoints
  - 5a Stent expansion at index procedure, MSA divided by the average reference area.
  - 5b In-stent late lumen loss up to 1 year, which is the decrease in MLA area from the index procedure

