### 7.3.1 Secondary Safety Sensitivity Analyses

Just as in the main analysis, if there are missing values in any of the safety datasets, 1, 1a, 1b, 1c, 2, 2a, 2b, or 2c, we will report the best/worst case bounds Gabriel et al. [5]. There will be no additional sensitivity analysis for the secondary efficacy endpoints.

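### Every secondary efficacy endpoint is confined to set A, so some results measured at the index procedure or at 1 year are left out, and no sensitivity analysis brings them back

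*SAP*

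**What the plan says.** Section 6 of the SAP states that set A "consists of all randomized participants who have a complete measure of the primary composite endpoint". It names three excluded groups. The first is a narrow class of withdrawals: "patients who withdraw consent prior to 1 year and explicitly do not wish to participate in the 1-year clinical follow-up data collection". The second rests on a decision by the adjudicators and covers "patients that are deemed to be lost to follow-up by the Clinical Endpoint Adjudication Board". The third concerns index imaging and covers "patients who lack baseline OCT or Quantitative coronary angiography".

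Section 7.3 uses set A for all secondary efficacy analyses (3a–3c, 4a–4c, 5a–5b), "to make the results comparable and on the same set as the primary". For the safety endpoints the same section takes the other course: "for safety we will use all available data", with a separate set for each endpoint in Section 6.

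Section 7.3.1 gives best-case/worst-case bounds for safety endpoints with missing values, then states: "There will be no additional sensitivity analysis for the secondary efficacy endpoints".

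**The concern.** Set A is defined by the composite, but its components become known at different times and from different sources. Stent delivery, residual stenosis and stent expansion ("Stent expansion at index procedure, MSA divided by the average reference area") are settled when the index procedure ends. Target vessel failure and its parts are clinical events that need no index imaging. Requiring the whole composite for each of them leaves out values that were measured.

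This does not match the questions in Section 3.1.2. For 3a–3c and 4a–4c these concern the patients as randomised, whatever later changes in status occur outside the endpoint. A comparison of stent delivery that depends on whether the patient stays in contact for the next year is selected after randomisation, in an open-label trial, when the data to avoid this exist.

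The SAP sees the hazard elsewhere. Section 7.1.2 accepts that set A may be anti-conservative if drop-out is related to outcome and differs between arms, and adds bounds for the primary endpoint. Secondary efficacy has no counterpart.

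**Working it through.** **1. What each exclusion removes** (Sections 3.1.1, 6, 7.3 and 7.3.1 side by side)

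| Reason for leaving set A | Measured results left out | Reported elsewhere? |
|---|---|---|
| Lost to follow-up, or withdrawal with refusal of 1-year data | 3a, 3b, 5a | No |
| No index imaging | 4a cardiac death | Yes, as 1a on all available data |
| No index imaging | 4b target-vessel infarction | Partly: counted in 1b (any infarction), without the target-vessel label |
| No index imaging | 3c target vessel failure, 4c revascularisation | No |

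**2. The SAP's own figures** (Section 8: 25% vs 10%, two-sided 0.05, 80% power). The unpooled formula gives (1.960 + 0.842)² × (0.25×0.75 + 0.10×0.90) / 0.15² = 96.8, so 97 per arm, as stated. Exact unconditional power by enumeration is 77.5% at 97 and 79.2% at 100 per arm with Fisher ordering, or 78.2% and 80.3% with mid-p ordering. The SAP states 78% and 80%. These figures neither support nor weaken the point. They supply only the 194 and the 200.

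**3. Number affected** (assumption). The SAP speaks of a low level of loss and gives no rate. (200 − 194)/200 = 3%. At 3%, 5%, 10% or 15% excluded, 6, 10, 20 or 30 of 200 patients leave every secondary efficacy analysis. For 3b and 5a this is an upper figure, because patients excluded for lack of imaging have no such value to lose.

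**4. Residual stenosis, 3b** (assumption: 20 of 100 in one arm, 3 excluded)

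| Excluded patients with residual stenosis | Reported in set A |
|---|---|
| 0 of 3 | 20/97 = 20.6% |
| 1 of 3 | 19/97 = 19.6% |
| 2 of 3 | 18/97 = 18.6% |
| 3 of 3 | 17/97 = 17.5% |

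If leaving is unrelated to outcome, the expected count among the 3 is 0.6, and (20 − 0.6)/97 = 20.0%, so there is no bias. The last row then has probability C(20,3)/C(100,3) = 1140/161700 = 0.7%.

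**5. Target vessel failure, 3c** (assumption: true risk 10%, 5 of 100 without index imaging, risk q among those 5). Set A shows (10 − 5q)/95:

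- q = 10%: 9.5/95 = 10.0%
- q = 30%: 8.5/95 = 8.9%
- q = 50%: 7.5/95 = 7.9%

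If 1 of 100 in the IVL arm and 5 of 100 in the conventional arm lack imaging, with q = 50% in both, set A gives (9.5/99)/(7.5/95) = 9.6%/7.9%, a risk ratio of about 1.2 where the truth is 1.0. This is a deliberately unfavourable example.

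**6. The same patients in the primary.** Residual stenosis of 20% or more is itself a composite event. If the 3 patients in the last row of step 4 are excluded, the primary loses them too: at the SAP's 25%, 25/100 becomes 22/97 = 22.7%. If they are instead kept because their composite is already decided, 3b does not move.

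**The case against.** The choice is deliberate and reasoned. Components reported on the same patients as the composite can be reconciled with it, and differing denominators make that harder. Nothing here is formally tested: Section 5 limits testing to the primary endpoint. Few patients are likely to be involved, and if they leave for unrelated reasons the estimates are not biased.

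Most of this stands, and it limits the size of the point. The comparability argument stands only in part. Set A does not give one common denominator, because a patient with quantitative angiography only can be in set A without an OCT stent area for 5a, and 5b needs 1-year OCT that set A does not require. Cardiac death already appears with two possible denominators, as 1a and 4a. A supportive set A table would keep the comparison.

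Some stronger readings are not supported:

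- A reader might infer that any withdrawal removes a patient. Section 6 removes only those who also refuse 1-year data collection, although loss to follow-up has the same effect.
- A reader might infer that every patient without index OCT is removed. Sections 3.1.1 and 7.1.2 let quantitative angiography stand in, so the natural reading is that both must be lacking. The wording in Section 6 does not settle this.
- A reader might infer that nothing on the imaging-excluded patients is reported. Their cardiac deaths and infarctions reach the report as 1a and 1b.
- A reader might take 3% as the SAP's stated loss rate, or the 2.5-point shift as expected. The first is an inference and the second a worst case.
- A reader might infer that the primary result is untouched in that worst case. Step 6 shows that it would lose the same events. That follows from the set A definition for the primary, for which Section 7.1.2 plans bounds.

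**Conclusion.** The point holds in a limited form. The SAP leaves out measured 3a, 3b and 5a results for patients later lost or refusing 1-year data. It also leaves out known 3c and 4c status, and the target-vessel label in 4b, for patients without index imaging. It rules out any sensitivity analysis that would show the effect.

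The size cannot be determined from the SAP. On an assumed 3% exclusion the effect runs from no bias, if exclusion is unrelated to outcome, to 20.0% reported as 17.5% in one arm at worst. The larger distortion in the target vessel failure example needs exclusion that differs between arms and strong outcome dependence. Only estimates and intervals of secondary endpoints are concerned, not the trial's type I error. It is an inexpensive improvement that should be made before the data are analysed.

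**What to change.** In Section 6, define efficacy sets 3a to 5b as is done for safety: all randomised patients with that endpoint measured, analysed by randomised arm. In Section 7.3, report 3a, 3b, 3c, 4a–4c and 5a on these sets, and keep the set A results as a supportive table for comparison with the composite. For the 1-year endpoints, state when status counts as measured, including for a patient with an event recorded before being lost. State also whether the imaging exclusion means lacking both OCT and quantitative angiography.

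The cost is a few lines of SAP text, one extra table and slightly different denominators between component rows, which the safety tables already accept. The change recovers measured values only and does not deal with values never obtained.
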